#### Statistics

Data from NIRS monitoring will be used to determine hemoglobin content changes in tibial bone from changes in light absorption on a moment-by-moment basis. A detailed description of the analysis can be found in our previous work. [12] Briefly, NIRS monitoring provides a change in hemoglobin content from one state to another. This is due to the fact that absolute intensity of the scattered light measured across the tibia cannot be used for an absolute measure of perfusion. However, as perfusion increases, there is a proportional increase in absorption (and vice versa). Thus, percent change in total hemoglobin detected reflects the relative change in perfusion.

The main outcomes assessed will be popliteal artery thickness and lumen diameter, tibial perfusion, and whole leg blood flow. This project will employ a simple and straightforward statistical approach to compare responses within and between groups. Statistical significance will be set at 0.05, and power at 80%. Descriptive statistics will be presented including mean, median, standard deviation, and range. Differences/relations will be considered as statistically significant at alpha=0.05 level. For all parametric statistical tests, conformity of data to required statistical assumptions will be verified using standard methods. If assumptions for parametric tests do not hold, non-parametric alternatives will be employed. The analysis plan is written as though there are no distributional problems; assumptions for all analyses will be checked and analogous methods calling for fewer and/or weaker assumptions will be used, if called for. For the data from aim 1, unpaired t-tests will be used to assess changes in perfusion between groups and reactive

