### II. SPECIFIC AIMS

- 1) Determine if popliteal artery structural changes are reflected in altered myogenic control of tibial bone perfusion post SCI.

*Hypothesis: Compared to able-bodied, those with SCI will demonstrate greater popliteal artery wall thickness and smaller diameter that will relate to both greater myogenic vasoconstriction (in response to leg dependency) and lesser myogenic vasodilation (in response to reactive hyperemia) in tibial bone.*

- 2) Determine if popliteal artery structural changes are reflected in lesser increases in tibial bone perfusion during compressive loading post SCI.

*Hypothesis: Compared to able-bodied, those with SCI will demonstrate greater popliteal artery wall thickness and smaller diameter that will relate to smaller increases in bone perfusion with increasing loading conditions.*

- 3) Determine if nitric-oxide mediated vasodilation is present in the tibial bone vasculature of able-bodied.

*Hypothesis: In able-bodied, the tibial bone vasculature vasodilates in response to a nitric oxide donor.*

All able-bodied volunteers will complete both aim1 and aim2. Only a subset of volunteers with SCI – those with time since injury between 3 and 24 months post injury – will be included for aim 2. The proposed study will investigate the control of bone perfusion in the SCI population as it relates to vascular remodeling and loading conditions.

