### III. SUBJECT SELECTION

#### **Inclusion criteria**

We anticipate we will recruit 29 individuals (males and females) aged 18 to 40 years with injuries, American Spinal Injury Association Impairment Scale (AIS) A and B and C. For aim 2, only individuals with SCI with complete injuries between 3 and 24 months post injury will be included. In addition, we will recruit 29 healthy individuals (males and females) age and gender matched to enroll for this study.

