### VI. STATISTICAL ANALYSIS

#### Sample Size

Our prior work found a borderline significant increase ( $p=0.06$ ) in tibial perfusion after exercise in able-bodied. Power analysis at 80% of these data showed that 17 subjects would have provided a  $p<0.05$  increase in perfusion. Therefore, for this study, we based our sample size on this calculation. We do not expect any sex-related difference; moreover, the SCI population is comprised primarily of males. To ensure a sufficient sample size for NO-mediated vasodilation, we will aim to recruit an additional of 17 individuals in each group. Therefore, we will recruit 29 individuals with SCI (men and women) and 29 healthy individuals (men and women) to participate in the study.

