## PARTNERS HUMAN RESEARCH COMMITTEE

### DETAILED PROTOCOL

hyperemia/leg dependency. Since the two conditions result in distinct and opposite responses, they should be considered separately. For the data from aim 2, for the three passive loading conditions (10%, 30%, 50% body weight without associated muscle contractions), a 2x3 ANOVA will be used to assess changes in perfusion between groups across loading conditions.

The results of this study will provide invaluable insights into bone perfusion in the paralyzed legs of those with SCI. For both aims, we anticipate that individuals with SCI will have less bone perfusion compared to able-bodied due to the extensive vascular maladaptations. Even if the results are not different between those with SCI and able-bodied, this study will have explored a potentially key contributor to SCI-related bone loss, with major implications in treating osteoporosis.

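### Controls are age and gender matched, but the aim 1 t-tests and the aim 2 ANOVA carry no term for the matching factors: aim 1 may lose some precision, and aim 2 has no assured age and sex balance

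*Combined protocol and SAP*

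**What the plan says.** All references are to the first protocol in the combined document (popliteal structure, loading and nitric oxide).

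- **Recruitment.** Section III, Inclusion criteria: "we will recruit 29 healthy individuals (males and females) age and gender matched to enroll for this study". The SCI group is also 29, aged 18 to 40. The section does not say whether matching is individual or by frequency, and gives no age tolerance and no pair identifier.
- **Aim 1 test.** Section VI, Statistics: "unpaired t-tests will be used to assess changes in perfusion between groups", with leg dependency and reactive hyperemia analysed separately.
- **Aim 2 test.** Same section: "a 2x3 ANOVA will be used to assess changes in perfusion between groups across loading conditions".
- **Who enters aim 2.** Section II has all able-bodied volunteers complete it, but "Only a subset of volunteers with SCI", namely those 3 to 24 months post injury. Section III adds that their injuries must be complete.
- **Error rates.** "Statistical significance will be set at 0.05, and power at 80"%. Sidedness is not stated.

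Nothing in Section VI refers back to the matching. The provision for weaker-assumption methods concerns the assumptions of the tests, chiefly distributional ones, and does not bring in age, sex or pairs.

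**The concern.** Matching makes the groups alike on age and sex by design. An analysis without those factors leaves whatever variance they explain in the error term, so the standard error of the group difference does not reflect the balance that recruitment achieved. In aim 1 the stake is precision.

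In aim 2 the issue is different. Controls matched to all 29 SCI participants are compared with only some of them. The balance that matching secured for the whole group need not hold for the subset, and the planned ANOVA has no term to absorb a difference.

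**Working it through.** **The plan's own figure.** Section VI, Sample Size, derives 17 subjects from a pilot increase with p=0.06 in able-bodied people. Pilot size, mean change and SD are not given, so 17 cannot be reproduced directly. Working back with a two-sided one-sample t-test, a pilot of 9 gives t = 2.19, a standardized change of 2.19/√9 = 0.73, and exactly 17 for 80% power. The figure is therefore plausible. It sizes a change within one group, however, and says nothing about power for the SCI versus control comparison. The check below starts from 29 per group.

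**Inputs.** n = 29 per group and alpha 0.05 come from the documents. Assumed: a two-sided test, and a within-pair correlation ρ of 0 to 0.3, because the documents give none. If matching on a factor is exact, ρ equals the share of response variance which that factor explains.

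**Standard error.** With SD σ in each group:

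- Unpaired: √(2σ²/n)
- Using the matching: √(2σ²(1−ρ)/n)
- Ratio: 1/√(1−ρ), that is 1/√0.9 = 1.054, 1/√0.8 = 1.118, 1/√0.7 = 1.195

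**Type I error and power.** The true difference is set at 0.749 SD, which gives the unpaired test 80% power at 29 per group when the groups are independent (56 df). Simulation, 200,000 trials per cell:

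| ρ (assumed) | Unpaired SE too large by | Unpaired type I error | Unpaired power | Paired power |
|---|---|---|---|---|
| 0 | 0% | 5.0% | 80.0% | 78.7% |
| 0.1 | 5% | 4.0% | 81.1% | 82.6% |
| 0.2 | 12% | 2.9% | 82.6% | 86.8% |
| 0.3 | 20% | 2.1% | 84.1% | 90.8% |

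At ρ = 0 the paired t-test is the worse choice. Its exact power is 78.6%, a loss of 80.0 − 78.6 = 1.4 points, because it has 28 degrees of freedom instead of 56. It breaks even with the nominal 80% at ρ of about 0.035.

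The size of the loss depends on the effect chosen. If the effect is instead set so that the paired test has 80% power, unpaired power is about 81.5%, 78%, 75% and 69% at the same four values of ρ.

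**Adjusting for age and sex instead of pairing.** Same difference of 0.749 SD, groups balanced on both factors, age explaining an assumed share of variance. There are 10,000 trials per cell, so simulation error is about √(0.8×0.2/10,000) = 0.4 points:

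| Share explained (assumed) | Unpaired power | Adjusted power | Gain (points) |
|---|---|---|---|
| 0 | 80.2% | 80.1% | about 0 |
| 0.1 | 81.2% | 84.0% | 2.8 |
| 0.2 | 82.5% | 87.8% | 5.3 |
| 0.3 | 85.0% | 92.1% | 7.1 |

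Type I error of the adjusted model stayed near 5% throughout.

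**Aim 2.** No arithmetic is possible, because the documents give neither the size of the SCI subset nor its age and sex mix. Side by side, Section III matches controls to the SCI group as a whole, Section II brings all controls but only part of the SCI group into aim 2, and Section VI compares the two without covariates. Balance is then neither secured by design nor restored by analysis.

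**The case against.** The strongest case against is that the matching factors may hardly matter here. The Sample Size section expects no difference between the sexes, ages span only 18 to 40, and the perfusion outcome is a within-person percent change, which removes at least part of any stable difference in level. A correlation near zero is plausible. The unpaired standard error would then be about right and nothing would be lost. Age and gender matched may also mean only that the groups are broadly similar, in which case calculations based on 29 one-to-one pairs do not strictly apply.

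Most of this stands. A reader might infer that the standard errors are too wide and that power is being lost. The documents do not support that as a fact: it requires age or sex to predict the response, which they do not establish. Nor should a reader infer that the unpaired test threatens validity in aim 1. With positive correlation its type I error is below 5%, and at the difference of 0.749 SD its power stays at or above 80%.

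A reader might likewise infer that the aim 2 comparison is biased. The subset is defined by time since injury and completeness, not by age or sex. Bias would need the subset to differ on those factors and the factors to affect perfusion, and neither is shown.

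The objection does not justify leaving the analysis as it is. The expectation about sex is silent on age. Adjustment costs essentially nothing if the factors are irrelevant, and it does not depend on which type of matching was meant.

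**Conclusion.** The point holds in conditional form. The plan matches on age and gender and then analyses as if it had not. If those factors explain 0 to 30% of the variance (assumed), the aim 1 standard error is overstated by 0 to 20%, type I error runs from 5.0% down to about 2.1%, and an age- and sex-adjusted model would gain about 0 to 7 points of power at a true difference of 0.749 SD. These figures rest on 29 per group, a two-sided 5% test and close matching. The loss is one of efficiency.

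For aim 2 the conclusion is only that balance is not assured and that an imbalance could enter the group effect. Its size and direction cannot be given from the documents.

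**What to change.** - **State the matching.** Say in Section III whether it is individual or by frequency, and with what age tolerance.
- **Aim 1.** Replace each unpaired t-test with a linear model of the response on group, age and sex, and report the adjusted group difference with its confidence interval.
- **Aim 2.** Add the same age and sex terms to the group-by-load model. As main effects they adjust the group difference averaged over loads. If the group-by-load contrast is to be adjusted too, the model also needs age-by-load and sex-by-load terms.
- **Prefer adjustment to a paired t-test.** It works for individual or frequency matching and keeps participants whose match has no usable data. It also avoids the 1.4-point loss at zero correlation.

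Cost: a change of wording. Age and sex are already needed for eligibility and matching, so there is nothing new to collect. In aim 1 the adjustment uses two degrees of freedom (56 to 54), with negligible loss of power if neither factor matters.

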## PARTNERS HUMAN RESEARCH COMMITTEE

### DETAILED PROTOCOL

hyperemia/leg dependency. Since the two conditions result in distinct and opposite responses, they should be considered separately. For the data from aim 2, for the three passive loading conditions (10%, 30%, 50% body weight without associated muscle contractions), a 2x3 ANOVA will be used to assess changes in perfusion between groups across loading conditions.

The results of this study will provide invaluable insights into bone perfusion in the paralyzed legs of those with SCI. For both aims, we anticipate that individuals with SCI will have less bone perfusion compared to able-bodied due to the extensive vascular maladaptations. Even if the results are not different between those with SCI and able-bodied, this study will have explored a potentially key contributor to SCI-related bone loss, with major implications in treating osteoporosis.

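### Aims 1 and 2 ask whether popliteal wall thickness and diameter relate to the tibial perfusion response, but no named test contains either structure variable

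*Combined protocol and SAP*

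**What the plan says.** All references are to the first protocol in the combined file, the one on arterial structure and loading.

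- **II. Specific Aims.** Both hypotheses have two halves. The first is that the SCI group has thicker walls and smaller diameters. The second is that these features are tied to the perfusion response: for Aim 1 they "will relate to both greater myogenic vasoconstriction (in response to leg dependency) and lesser myogenic vasodilation", and for Aim 2 they "will relate to smaller increases in bone perfusion with increasing loading conditions".
- **V. Study Procedures.** The introductions to the leg dependency/reactive hyperemia block and to the loading block both give the link between popliteal structure and the perfusion response as the reason for the procedure.
- **VI. Statistical Analysis, Statistics.** "The main outcomes assessed will be popliteal artery thickness and lumen diameter, tibial perfusion, and whole leg blood flow". On inference: "Differences/relations will be considered as statistically significant at alpha=0.05 level". Then the two named analyses. Aim 1: "For the data from aim 1, unpaired t-tests will be used to assess changes in perfusion between groups", with leg dependency and reactive hyperemia kept apart ("Since the two conditions result in distinct and opposite responses, they should be considered separately"). Aim 2: "a 2x3 ANOVA will be used to assess changes in perfusion between groups across loading conditions".
- **Same section, expected result.** "we anticipate that individuals with SCI will have less bone perfusion compared to able-bodied due to the extensive vascular maladaptations".

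**The concern.** The question of both aims is a relation between two measured quantities, while both named tests compare one of those quantities between groups. A reader who followed the plan to the letter would finish with a group difference in perfusion, or none, and no estimate of how perfusion varies with thickness or diameter. The first half of each hypothesis, the group difference in structure, has no named test either.

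Two things are at stake. First, attributing lower perfusion in SCI to vascular changes would rest on two group differences placed side by side, only one of which has a named test. Second, the model for the relation would be chosen after the data are seen. There are two structure variables, two Aim 1 conditions, three loads, and a choice between pooled, group-adjusted and within-SCI analysis. These choices can give different answers.

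**Working it through.** **1. Variables in each named test.**

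| Analysis | Response | Factors | Thickness or diameter? |
|---|---|---|---|
| Aim 1, unpaired t-tests | change in perfusion | group | no |
| Aim 2, 2x3 ANOVA | change in perfusion | group, load | no |

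Structure appears in 0 of 2. The second protocol in the file does not measure popliteal structure, so it does not fill the gap.

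**2. The plan's own figure.** The only calculated sample size is 17, for an increase in perfusion after exercise in able-bodied people. It does not involve structure. It cannot be reproduced, because the earlier study's size, mean and SD are not given. It is attainable: an assumed 9 earlier subjects with two-sided p=0.06 lead to 17 for a paired t-test at 80% power. Nothing below depends on it.

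**3. What the Aim 1 t-test says about the relation.** By construction, nothing, since it does not use the structure variable. As an illustration (simulated, 29+29, assumed 0.75 SD group difference in perfusion), it is significant in 80% of trials whether the within-group correlation is 0, 0.3 or 0.5.

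**4. Why the unnamed model matters.** Assume no within-group relation and a group shift of d SD on both variables. The expected pooled correlation is (d²/4)/(1+d²/4). Simulated at 29+29, two-sided 0.05:

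| Assumed d | Expected pooled r | Pooled correlation significant | Group-adjusted slope significant |
|---|---|---|---|
| 0.5 | 0.0625/1.0625 = 0.06 | 7–8% | 5% |
| 0.75 | 0.1406/1.1406 = 0.12 | 15% | 5% |
| 1.0 | 0.25/1.25 = 0.20 | 33–34% | 5% |

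**5. Detectable association.** Two-sided 0.05 (sidedness is not stated, so assumed), 80% power, k adjusting variables: r = tanh((1.960+0.842)/√(n−3−k)).

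- Aim 1, both groups, group in the model (n=58, k=1): 2.802/√54 = 0.381, so partial r = 0.36.
- Within SCI (n=29, k=0): 2.802/√26 = 0.549, so r = 0.50.
- Aim 2, one summary per person, 29 able-bodied plus an assumed 29, 17 or 12 SCI (n=58, 46, 41; k=1): partial r = 0.36, 0.41, 0.43. The size of the SCI subset is not stated.
- With Holm over four Aim 1 slopes, the first step (0.05/4 = 0.0125) raises 0.36 to 0.43, and 0.50 to 0.57 within SCI.

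**6. Two checks on the shape of the repair.**

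- *Aim 1, relation present only in SCI* (assumed r=0.5, 29+29). The common group-adjusted slope is significant in 47% of trials and the within-SCI correlation in 81%. A common slope alone could hide such a relation.
- *Aim 2, structure effect equal at all three loads* (assumed slope 0.5 SD per SD, intra-person correlation 0.5, group shift 0.75 SD; 29 able-bodied with 29, 17 or 12 SCI). The loads of 10, 30 and 50% are equally spaced, so the linear trend is the 50% minus the 10% response, and an equal effect cancels. Structure by linear load is significant in about 5% of trials, the group-adjusted structure main effect in 95–99%.

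**The case against.** The best defence is that the plan does not ignore structure. Thickness and lumen diameter are main outcomes, relations are given an alpha level, and the general statement about comparing responses within and between groups could be read to cover a group comparison of structure. The study is mechanistic, every variable is collected, and nothing is lost if the model is written down later. This stands as far as intent goes, and a reader who infers that the relation was forgotten goes too far. It does not supply a model, a predictor or an analysis group.

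Other stronger readings are also unsupported:

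- *That the plan would use a misleading pooled correlation.* The documents propose none. The percentages in step 4 describe one way of filling the gap, under assumed shifts, and the risk is small at about 0.5 SD or less.
- *That the plan already draws a causal conclusion.* The sentence on vascular maladaptations states what the authors anticipate. The point is that the named tests could not support it.
- *That one estimand is the only right one.* The aims are framed around people with SCI, so a within-SCI slope is as defensible as a group-adjusted one. For Aim 2, the wording allows both the size of the increase and its change with load. Holm is also an option, not something the documents require.
- *That 29 per group is too few.* No expected correlation is given, so this cannot be judged.

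**Conclusion.** The point holds. Two aims state a relation between arterial structure and perfusion, and neither named test contains a structure variable. That conclusion comes from the text and needs no assumption. It is more than missing detail, because the named tests, carried out exactly, leave both aims unanswered.

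The numerical consequences are conditional. The pooled-correlation rates rest on assumed equal shifts in both variables. The 47% against 81%, and 5% against 95–99%, rest on the assumed effects stated with them. The detectable r values rest on full recruitment of 29+29 and two-sided testing and, for Aim 2, on assumed subset sizes.

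**What to change.** Keep the planned t-tests and ANOVA, and add the following to Statistics before the data are analysed:

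1. **Structure.** Compare wall thickness and diameter between groups, which tests the first half of both hypotheses.
2. **Aim 1.** For leg dependency and reactive hyperemia separately, regress the perfusion response on thickness, and in a second model on diameter, with group in the model. Test the group-adjusted structure slope. Report the group-by-structure term and the within-SCI slope beside it.
3. **Aim 2.** Fit a mixed model with a participant effect, load as a within-subject factor (each person receives all three loads), group, group by load, structure and structure by load. Test the structure main effect (size of the increase) as well as structure by load (change with load).
4. **Choices to state.** Say which slope is primary and whether a multiplicity adjustment such as Holm applies. Both are the sponsor's choice. Rule out a correlation pooled over groups without group in the model.
5. **Precision.** Give the detectable association from step 5 of the working, and the expected size of the Aim 2 SCI subset.

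The cost is wording and a few degrees of freedom, with no new measurement. The adjusted slope sets aside association that lies only between groups, the within-SCI slope needs a larger r, and Holm, if chosen, raises the thresholds further. A significant slope would still be an association, so the text on expected results should be worded to match.

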#### **VII. RISKS AND DISCOMFORTS**

The tibial bone loading device should pose minimal risks – the device applies loading at loads less than full body weight – from 10% to 50% body weight. This should pose minimal risk to volunteers with SCI since they will be less than 40 years of age and within 2 years of injury and so should have minimal risk of osteoporosis. Cuff inflation might result in muscle discomfort that will quickly go away after cuff release. In those with SCI, cuff inflation can also cause autonomic dyreflexia. The NIRS system is non-invasive and poses little risk to the patients. Initial trials showed minor reddening of the skin; however, this was temporary and it quickly went away. Nitroglycerin (0.4 mg Nitroglycerin sublingual) at the small doses given is considered low risk, and any higher risk patients are excluded during the eligibility process. Sublingual nitroglycerin may result in headaches, weakness, dizziness, lightheadedness, nausea, mild burning or tingling with the tablet in the mouth, and flushing (warmth, redness, or tingly feeling under the skin) as the body adjusts to the medication. Some serious but unlikely side effects include fainting and fast and irregular heart rate. Blood pressure and heart rate will be monitored continuously, and the nitroglycerin will be removed immediately if large declines in blood pressure (>20 mmHg) occur.

